5.2.2 Mode of action

IMU-838 is a small molecule investigational drug (vidofludimus calcium) under Phase 2 development as an oral tablet formulation for the treatment of relapsing-remitting multiple sclerosis, inflammatory bowel disease and other chronic inflammatory and autoimmune diseases.

IMU-838 selectively inhibits the human enzyme dihydroorotate dehydrogenase (DHODH), a key enzyme of pyrimidine *de novo* biosynthesis. Highly metabolically activated cells, such as hyperactivated lymphocytes in chronic inflammatory diseases, malignant transformed cells in cancer as well as virus infected cells, are highly dependent on DHODH. [1] In these cells, the

extraordinary demand of nucleotides cannot be sufficiently supported by recycling of nucleotides and therefore, the de novo synthesis of pyrimidines needs to be activated.

Inhibition of de novo pyrimidine biosynthesis is a well-recognized antiviral mechanism. The presumptive explanation is attributed to the direct depletion of host nucleosides necessary for replication of the viral genome; however, secondary activation of the innate immune response has also been described as a relevant downstream mechanism. Therefore, DHODH inhibition ameliorates and blocks the viruses' ability to "hijack" the human host cell mechanisms of ribonucleic acid (RNA) production as a means to virus replication. This is a host cell mechanism with the advantage that it has broad viral activity, is not influenced by resistances or mutations of the virus and can be combined with other antiviral drugs targeting the virus itself. This direct, broad-spectrum antiviral effect has been observed in various virus infected cells, such as influenza virus infections, cytomegalovirus infections and even hemorrhagic fever-causing viruses, such as Lassa virus. Treatment with IMU-838 may also avoid virus reactivation of further clinically relevant viruses.

In addition to its antiviral activity, IMU-838 exhibits strong anti-inflammatory activities by selectively targeting activated lymphocytes, which express DHODH at high levels to satisfy their need for de novo pyrimidine synthesis. Resting lymphocytes and bone marrow cells satisfy their pyrimidine requirements through a DHODH-independent salvage pathway. The metabolic stress secondary to DHODH inhibition leads to a reduction of pro-inflammatory cytokine release including IL-17 (IL-17A and IL-17F) and interferon gamma (IFN γ), and to an increased apoptosis in activated lymphocytes. [2] IMU-838-mediated DHODH inhibition does not induce unselective immunosuppression.

One key advantage of DHODH inhibition is that it primarily targets metabolically active cells, and therefore may not negatively impact "normal" cells in a substantial fashion. In addition, no increased rates of neutropenia or other major antiproliferative effects as compared to placebo have been observed.

IMU-838 is further characterized by a short blood half-life of 30-40 hours making it ideal for once-daily dosing and resulting in only little accumulation after daily dosing (steady state concentrations are reached within 4-8 days with an accumulation factor of 2). Importantly due to the short blood half-life, the wash-out period for IMU-838 is considerably shorter than for teriflunomide.

5.2.3 Non-clinical studies

Pharmacodynamics

Vidofludimus strongly inhibits activated lymphocytes and reduces the release of pro-inflammatory cytokines and other physiologic effects of activated lymphocytes in *in-vivo* studies.

Vidofludimus demonstrated broad-spectrum antiviral activity *in-vitro* at concentrations below therapeutic blood levels achieved in treated patients.

- In cell culture experiments vidofludimus inhibited the viral replication of the human immunodeficiency virus (HIV) and hepatitis C virus (HCV).
- Reverse transcriptase activity and the appearance of the specific HIV antigen p24 was evaluated in human peripheral blood mononuclear cells (seronegative for HIV and hepatitis B virus) that were infected *in vitro* with HIV-191US005 and incubated with various vidofludimus concentrations. These experiments demonstrated a median effective dose (ED₅₀) of vidofludimus of approximately 2 μ M.
- In a human hepatoma cell line (Huh7) harboring an HCV sub genomic replicon, vidofludimus reduced replicon levels with a median ED₅₀ of 4.64 μ M.
- Vidofludimus was active against viruses of the herpes family. In an infection model of human fibroblasts infected with human cytomegalovirus (hCMV), vidofludimus showed an activity of around 7.4 μ M. This activity was within the same range of Ganciclovir which is used in clinical practice to treat hCMV.
- Vidofludimus demonstrated activity against mammalian Arena virus infections, the RNA virus causing human hemorrhagic fever diseases like Lassa fever, with an IC₅₀ (concentration causing 50% inhibition) of 2.8 μ M. In this case, DHODH inhibition mediated effects were independent of IFN signaling.

Based on *in-vitro* data, vidofludimus was primarily metabolized via cytochrome P450 (CYP)2C8 with smaller contributions by CYP2C9. Vidofludimus is primarily eliminated via feces (about 70%).

Vidofludimus mildly to moderately inhibits several transport systems, including the urate anion transporter 1 (URAT1), the breast cancer resistance protein, the organic anion transporters 1 and 3, the organic anion transporting polypeptides 1B1 and 1B3, and the bile salt export pump.

5.2.4 Clinical trials

So far, no clinical trials investigating the antiviral activity of vidofludimus have been performed. However, several studies were or are investigating vidofludimus in the treatment of autoimmune and chronic inflammatory diseases.

Two clinical trials investigated the beneficial effects of 4SC-101, the previous vidofludimus free acid formulation, in patients with rheumatoid arthritis (RA). 4SC-101 improved various clinical parameters versus placebo. A pronounced effect was observed for inflammatory parameters.

In a small Phase 2 trial in patients with corticosteroid-dependent inflammatory bowel disease (Crohn's disease and ulcerative colitis), 4SC-101 showed beneficial effects in the remission

maintenance therapy. Compared with historical placebo data, 4SC-101 treatment showed a significantly higher response rate (88.5% total response) as well as a corticosteroid sparing effect.

No 4SC-101-associated clinically significant adverse reactions were observed at doses of <70 mg once daily including the potential target organs liver and kidney as identified in non-clinical or early clinical trials. At higher 4SC-101 doses (>70 mg/day or single doses of 210 mg) potential drug-related increases of red blood cells (RBC) in urine and hematurias were observed (see also Section 8.3).

Two Phase 1 clinical trials were performed for calcium vidofludimus (IMU-838). In Trial P1-IMU-838-SAD, doses from 10 to 40 mg IMU-838 resulted in dose-linear blood pharmacokinetics (PK) under fasted conditions. For the 30 mg dose (the dose expected to be closest to an effective dose), the terminal plasma half-life was approximately 40 hours and the median concentration peaked at 5 hours. Comparing single dosing of 10 mg under fasted and fed conditions, no detrimental effect of food intake was found. Single oral doses of 10 to 40 mg IMU-838 were well tolerated. No adverse events (AEs) of e.g., hematuria or clinically significant RBC in urine high were observed in that clinical trial.

In Trial P1-IMU-838-MAD, repeated oral dosing of IMU-838 over 14 days in doses from 30 to 50 mg resulted in dose-proportional blood PK under fasted conditions. Geometric mean half-life at steady state ranged from 28.6 to 30.4 hours. Overall, median peak concentration following multiple oral doses of IMU-838 occurred between 2 to 3 hours after the first and after repeated dosing. Steady-state levels were reached within about 4 days for 25 mg IMU-838, within 6-8 days for 30 mg, within about 6 days for 40 mg, and within about 8 days for 50 mg IMU-838. Repeated once-daily oral doses of 30 to 50 mg IMU-838 over 14 consecutive days were well tolerated. Mild or moderate treatment-emergent adverse events (TEAEs) were reported by 31 subjects (59.6%); overall 53 TEAEs, reported by 29 subjects (55.8%) were considered drug-related. The number of subjects with drug-related TEAEs or the number of drug-related TEAEs did not increase with increasing dose.

Most individual laboratory values were within the normal ranges. There were no clinically relevant differences between pre- and post-dose assessments and between the treatment groups for any parameter.

Currently ongoing studies with IMU-838 include 2 double-blind, randomized, placebo-controlled Phase 2 trials in patients with ulcerative colitis (CALDOSE-1) and relapsing-remitting multiple sclerosis (EMPHASIS). The primary objective of the ulcerative colitis trial is to determine the optimal dose of IMU-838 to induce symptomatic remission and endoscopic response in patients with moderate-to-severe disease. The primary objective of the multiple sclerosis trial is to evaluate the efficacy of IMU-838 based on magnetic resonance imaging assessments in the treatment of relapsing-remitting multiple sclerosis. Results of an interim analysis of the ulcerative colitis trial,

analyzed by an unblinded independent Data Review Committee showed that none of the doses used (10 mg, 30 mg, or 45 mg) was likely ineffective or intolerable. In addition, there is an ongoing open-label investigator-sponsored trial using IMU-838 in patients with progressive sclerosing cholangitis conducted in the USA under an Investigator IND.

5.2.5 Safety of IMU-838

At this time and counting both formulations, more than 500 human subjects and patients have been exposed to the active moiety of IMU-838, i.e., vidofludimus. Of these, 299 were dosed with 4SC-101 and approximately 360 with IMU-838 (some of the studies are still blinded and total exposure to IMU-838 can therefore only be estimated).

The safety analysis of all exposed subjects provided the following findings:

- No deaths
- No serious adverse event (SAE) during Phase 1 with IMU-838
- The most frequent AEs for IMU-838 during Phase 1 were:
 - Headache
 - Flatulence
 - Common cold
 - Positive urine dipstick for hemoglobin

IMU-838 is a selective DHODH inhibitor and did not inhibit any kinase (of a panel of over 100 tested protein kinases) at blood concentrations that are found at therapeutic dose levels. However, IMU-838 inhibits organic anion transporters such as URAT1, which potentially could affect renal uric acid elimination.

In conclusion, IMU-838 is expected to have a favorable safety profile, as in more than 400 patients (with RA, multiple sclerosis, or inflammatory bowel disease) or volunteers no increased events of diarrhea, nausea, alopecia or headache as well as no increases in abnormal liver function tests were observed.

5.3 Rationale for the trial

Acute viral infections, such as influenza virus, Ebola virus, and SARS-CoV-2 are an increasing and probably lasting health risk. [7] Broad-spectrum antivirals are clinically needed for the effective control of emerging and re-emerging viral infectious diseases. [9] However, besides intensive efforts to find therapeutic antiviral agents to manage such emergencies, reports on specific and effective drugs or vaccines with low toxicity are rare. [8] Thus, currently, there are no effective treatments against the new coronavirus SARS-CoV-2.

Literature data

Strong activity of DHODH inhibitors against SARS-CoV-2 *in vitro* were recently reported by Xiong et al. [9] However, established DHODH inhibitors show either an unfavorable PK profile (leflunomide/teriflunomide) or intolerable toxicity (leflunomide/Brequinar) and thus are not suitable as acute antiviral treatments. New DHODH inhibitors seem promising, although for most no animal or human safety data are available.

Xiong et al. [9] also demonstrated that a combination of DHODH inhibitors with antiviral drugs may improve therapeutic effects. Direct-acting antivirals, which target the viral replication cycle, are primarily effective in the early phase of infection while DHODH inhibitors which target a host cell factor, may also be effective in middle-to-late phases of infection or in patients with advanced respiratory disease.

DHODH inhibition selectively targets activated inflammatory and virus infected cells because normally growing cells are not substantially affected (see Section 5.2.2). For normally dividing cells, DHODH inhibition does not produce general immunosuppression. It was shown for teriflunomide that patients can be even vaccinated under therapy. [10, 11] DHODH inhibition by IMU-838 did not suppress bone marrow cells or inhibit fast-growing cells. In preclinical and clinical studies, IMU-838 did not show any off-target effects, such as neutropenia, diarrhea or alopecia, at rates that were above placebo.

A strong antiviral effect of DHODH inhibitors was described for several RNA and deoxyribonucleic acid viruses including Ebola [12,13], HIV [14], HCV [14], hCMV [15,16] and Influenza [14] viruses. While DHODH inhibitors are effective up to 12-16 hours after infection in *in-vitro* assays, other antiviral drugs can inhibit viral infection only up to 4 hours. [14,17]. DHODH inhibitors show a direct and an indirect antiviral effect both of which are linked to blocking pyrimidine de novo synthesis. In the direct pathway, the reduction of pyrimidine neosynthesis interferes with the viral transcription and replication. [14] However, the main antiviral effect might rather be an indirect effect via the induction or amplification of interferon-stimulated genes due to the reduced pyrimidine synthesis. [18] A large fraction of these genes plays a role in the host innate immune defense to viruses. While these genes are normally induced by interferons, the upregulation of these genes by DHODH inhibitors is independent of interferons. [12,18-20]

Antiviral activity of IMU-838 against SARS-CoV-2

Antiviral activity against SARS-CoV-2 of IMU-838 was investigated *in-vitro* in Vero 76 cells in a cytopathic effect assay. The virus was prepared in test media (Minimum Essential Media with 2% fetal bovine serum and gentamicin) to achieve the lowest possible multiplicity of infection that would yield >80% cytopathic effect within 5 days. Plates were infected prior to preparation and addition of compounds. IMU-838 was dissolved in dimethylsulfoxide to achieve a 100 mM stock and was serially diluted two-fold in media and added to the 80-100% confluent cell layer in triplicates, reaching a final concentration in the well starting from 100 µM down to 0.78 µM.

Controls in infected cells were M128533 (a protease inhibitor) as positive control and no treatment as negative control. The positive control performed as expected.

IMU-838 exhibited antiviral activity with an EC₅₀ (concentration that prevents 50% of virus induced cell death in virus infected cells) of 5.7 µM. For reference, the average trough levels of IMU-838 at steady state conditions is expected to be approximately 17 µM using the dosing regimen of 45 mg IMU-838 proposed for this trial.

Conclusion

Based on these data and the pharmacodynamics of vidofludimus, IMU-838 may represent a novel and efficacious oral treatment option for COVID-19 combining a broad antiviral activity with a selective anti-inflammatory effect. It is also important that IMU-838 is not known to cause any neutropenia for a patient population where decrease of neutrophils and lymphocytes is a critical feature of the disease.

6 Investigators, trial administrative structure, and committees

The clinical trial is funded by Immunic AG and it is planned to include about 10 to 45 centers in the European Union, Bosnia and Herzegovina, Moldova, North Macedonia, Russia, Ukraine, and USA (and as back up countries: Croatia and Serbia). [name], Stanford University, School of Medicine will be the coordinating investigator.

The Sponsor will reserve the right to define maximum number of patients per site and country to ensure a balance per site and country regarding enrolled patients. For Part 1, the number of patients per center is limited to 100 patients, and the number of patients per country is limited to 160 patients. These limits may be re-evaluated if the trial is expanded into Part 2.

The Sponsor, Immunic AG, will be responsible for the overall supervision and administration of the trial. Data management, statistical analysis and medical writing services will be done by FGK Clinical Research GmbH, München, Germany (a contract research organization [CRO]). Further vendors include:

- LKF - Laboratorium für Klinische Forschung GmbH, Schwentiniertal, Germany: central clinical safety laboratory
- SCRATCH Pharmacovigilance GmbH & Co. KG, Butzbach, Germany: pharmacovigilance services.
- Covance Central Laboratory Services, Geneva, Switzerland and Indiana, USA: central virology laboratory

Outside vendors will also be used for global and local project management, monitoring services, pharmacokinetics and IMP labeling, packaging, and distribution.

An **Independent Data Monitoring Committee (IDMC)** will be established to safeguard the interests of trial participants and to provide recommendations on trial conduct and sample size (for more details refer to Section 18). The IDMC will also fulfill the designated functions of a Data Safety Monitoring Board.

Addresses and telephone numbers of main responsible parties involved in the conduct of the trial are provided in Section 2.

7 Trial objectives and endpoints

Objective	Endpoint
Primary 
To evaluate the efficacy of IMU-838 plus investigator's choice of standard of care therapy (SoC) vs placebo plus SoC in the treatment of coronavirus disease 2019 (COVID-19) based on the need for invasive ventilation (INV) up to 28 days	
Proportion of patients without any need* for INV until end-of-study (EoS)
Key secondary 
To evaluate the efficacy of IMU-838 (+SoC) vs placebo (+SoC) in the treatment of COVID-19 based on surviving patients without respiratory failure, the duration of hospitalization in intensive care unit (ICU) and all-cause mortality up to 28 days	
Proportion of patients surviving without respiratory failure (defined as any need of ICU, INV, high-flow oxygen or extracorporeal membrane oxygenation [ECMO*] until EoS)Duration of ICU treatment until EoS28-day all-cause mortality

Trial objectives and endpoints (continued)

Objective	Endpoint
Secondary	
Efficacy	
 • To evaluate the efficacy of IMU-838 (+SoC) vs placebo (+SoC) in the treatment of COVID-19 based on a variety of further variables and time points (e.g., clinical status, renal impairment, oxygenation, hospitalization, concomitant vasoactive treatments, clinical recovery) • Time to clinical improvement, defined as the time from first dose of investigational medicinal product (IMP) to an improvement of at least 2 points on the WHO 9-category ordinal scale [21], or live discharge from hospital without oxygen supplementation, whichever comes first • Duration of hospitalization (for US sites only: or treatment in special outpatient setting in lieu of hospitalization due to resource restraints) • Proportion of patients 
 • free of renal-replacement therapy (RRT)[*] until EoS • free of ECMO[*] until EoS • free of INV until Days 6 and 14* • free of RRT until Days 6 and 14* • free of ECMO until Days 6 and 14* • with improvement of at least 2 points (from randomization) on the 9-category WHO ordinal scale [21] on Days 6, 14, and 28

Trial objectives and endpoints (continued)

Objective	Endpoint
Secondary (continued)	
Efficacy (continued)	
 • Proportion of patients 
 • with auxiliary oxygen therapy* (including all types of oxygen therapy) until Days 6, 14, and 28 • with clinical recovery defined as 
 • Axillary temperature ≤ 36.6 °C, or oral temperature ≤ 37.2 °C, or rectal or tympanic temperature ≤ 37.8 °C; and • Respiratory frequency ≤ 24 times/min without oxygen inhalation; and • Oxygen saturation $\geq 98\%$ without oxygen inhalation • With clinical improvement, defined as an improvement of at least 2 points on the WHO 9 category ordinal scale [21], or live discharge from hospital without oxygen supplementation, whichever comes first • Change in daily clinical patient status on the WHO 9-category ordinal scale [21] • Duration of INV • Duration of ECMO • Duration of RRT • Duration of auxiliary oxygen therapy (including all types of oxygen therapy) • Duration of hospitalization for survivors • Rate of ICU* admission until Days 6, 14, and 28 • Hospital-free days

Trial objectives and endpoints (continued)

Objective	Endpoint
Secondary (continued)	
Efficacy (continued)	
	
 • Time from IMP treatment initiation to death • Time to first prescription of INV • Time to first prescription of RRT • Time to first prescription of ECMO • Time to first prescription of INV, RRT, and ECMO • Time to ICU admission • Cumulative dose of vasoactive therapies and days (daily until Day 14) with vasoactive therapies (until Day 14) • Time to clinical recovery
Pharmacokinetics	
To evaluate trough plasma levels of IMU-838	
 • Morning trough plasma levels of IMU-838 on Days 0, 1 through 6, 14, and 28 • Correlation of trough levels (quartiles) to selected clinical outcomes
Safety	
To evaluate safety and tolerability of IMU-838	
 • AEs and SAEs • Vital signs • Clinical laboratory parameters (blood chemistry, hematology, and urinalysis) • Electrocardiogram (ECG) parameters • Temperature

Trial objectives and endpoints (continued)

Objective	Endpoint
Secondary (continued)	
Disease markers	
To explore blood levels of disease markers	
 • D-dimer • Lactate dehydrogenase (LDH) • C-reactive protein (CRP) • Troponin I (cTn) • Procalcitonin (PCT) • Correlation of disease markers to selected clinical outcomes
	The analysis for all endpoints includes absolute values and absolute change from Baseline over time; for LDH log transformed values will be used.
Virologic markers, biomarkers, and serologic markers	
To explore viral titers, measures of viral virulence and inflammatory markers	
Virologic markers
 
 • Severe Acute Respiratory Syndrome Coronavirus Virus (SARS-CoV-2) mean viral load - log10 copies in spontaneous sputum and nasopharyngeal swab samples 
 • Decrease of SARS-CoV-2 viral load • Time course of SARS-CoV-2 viral load • Qualitative virologic clearance in spontaneous sputum and nasopharyngeal swab samples (= 2 consecutive negative SARS-CoV-2 reverse transcriptase polymerase chain reaction [RT-PC] tests at least 24 hours apart) • Rate of conversion to a negative SARS-CoV-2 (qualitative) test on Days 6, 14 and 28 • Time to conversion to a negative SARS-CoV-2 (qualitative) test

Trial objectives and endpoints (continued)

Objective	Endpoint
Secondary (continued)	
Virologic markers, biomarkers, and serologic markers (continued)	
Biomarkers
 
 • Interleukin (IL)-17, IL-1β, IL-6, interferon gamma (IFNγ), tumor necrosis factor alpha (TNFα) 
Serologic markers
 
 • IgA and IgG antibodies against SARS-CoV-2 • Time to appearance of IgA and/or IgG antibodies • Proportion of patients with IgA and/or IgG antibodies on Days 6, 14, and 28
The analysis for all endpoints includes absolute values, relative and absolute change from Baseline over time, if applicable.	

* Patients who are assessed by the investigator to have a medical need of the respective treatment (i.e., INV, ECMO, RRT, ICU, hospitalization) but do not receive these treatments for other reasons will be counted for this endpoint.

8 Trial design and design rationale

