	Under pharmacokinetic endpoints: indicated that morning plasma trough values of IMU-838 will be measured at Days 0, 1 through 6, 14, and 28 (instead of Days 0, 1, 2, 3, 6, 14 and 28) to be consistent with Table 1	✓	✓		
	'Proportion of patients surviving without respiratory failure' added as key secondary endpoint and respective objective	✓	✓	✓	✓

Sections affected	Change	Applicable for Version			
		2.0 (DE)	2.1 (BG)	2.1 (USA)	2.1 (DE)
1, 7 (continued)	
Following secondary endpoint changed as indicated: 'Cumulative dose of vasoactive therapies (daily until Day 14) and days with vasoactive therapies (daily until Day 14)'
 
Following secondary endpoint corrected as indicated: 'Proportion of patients with clinical improvement, defined as the time from first dose of IMP to an improvement of at least 2 points on the WHO 9-category ordinal scale....'',
 
For the secondary endpoint 'Proportion of patients with auxiliary therapy, indicated that the need of auxiliary oxygen therapy is sufficient for this endpoint and clarified that this proportion will be assessed not on but until Days 6, 14, and 28
 
For the secondary endpoint 'Rate of IC admission' clarified that this proportion will be assessed not on but until Days 6, 14, and 28
	✓	✓	✓	✓
1, 8.1	
Clarified that early safety analysis will be performed after 30 patients have completed Day 28. For US centers only, enrollment will be paused in the US at this time until after the IDMC has reviewed trial safety stopping criteria for the trial.
 
Safety follow-up added
 
For consistency reasons 'early interims safety analysis' replaced by 'early safety analysis'
	✓	✓	✓	✓
1, 8.1, 9.1, 16.1, 16.3.1, 16.4	
Sections updated to reflect the following as applicable:
 
 Specified that Part 1 and Part 2 will be handled as independent parts and respective changes in analysis, sample size and trial conduct described Alpha level for Part 2 changed from 0.05 to 0.025 (1-sided); information rate from 20% ($\alpha<0.0001$) to 50% ($\alpha=0.0026$) Sample size calculation adjusted 	✓	✓	✓	✓
1, 9.2 (Inclusion Criterion 1)	Included that the potential extension of the trial to include children after the MA1 will only be implemented after the approval of a respective protocol amendment	✓			

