9.2 Inclusion criteria

1. Male or female patients at least 18 years old (may only be extended to include children 12 years or older after MA1 following approval of a protocol amendment)
2. Admitted to the hospital or other medical in-patient treatment facility for treatment of COVID-19

The hospitalization needs to be for medical reasons (treatment of COVID-19 disease) and cannot be for social reasons or due to housing insecurity.

For US sites only: If the investigator would commonly hospitalize the patient but for healthcare resource reasons decides to treat the patient in a specially designed out-patient setting, then such patients are also allowed to enter the trial (please note that in this case the patient would be counted as clinical status category 3). The investigator then must assure that the patient has at least a twice daily assessment by qualified trial personnel and all laboratory assessments can be adequately performed as per protocol. The Sponsor reserves the right to discontinue this option via administrative letter if such assurances cannot be met by any site.

3. SARS-CoV-2 infection confirmed by reverse transcriptase polymerase chain reaction (RT-PCR) test in a nasopharyngeal, oropharyngeal or respiratory sample at ≤ 4 days before randomization
4. Moderate COVID-19 disease defined as fulfilling clinical status category 3 or 4 on the WHO 9-point ordinal scale [21]:
 - Category 3: Hospitalized (see note above for US only), virus-positive, no oxygen therapy with the following condition:
 - The hospitalization needs to be for medical reasons (treatment of COVID-19 disease) and cannot be for social reasons or due to housing insecurity
 - Category 4: Hospitalized, virus-positive, oxygen by mask or nasal prongs (excluding high-flow oxygen therapy) with the following conditions:

- Peripheral capillary oxyhemoglobin saturation (SpO_2) >92% at maximum of 6 liters oxygen flow per minute
- Stable respiratory rate ≤ 30 breaths/min at maximum of 6 liters oxygen flow per minute

5. Presence of at least 1 symptom characteristic for COVID-19 disease i.e., fever, cough or respiratory distress

6. Willingness and ability to comply with the protocol

7. Written informed consent given prior to any trial-related procedure

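### The cumulative auxiliary-oxygen endpoint is settled at entry for every WHO Category 4 patient, so it carries treatment information only from Category 3; clinical recovery has a lesser, unquantified baseline problem

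*Combined protocol and SAP*

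**What the plan says.** **Oxygen.** The secondary efficacy list in Section 7, repeated in Section 1, includes the proportion of patients "with auxiliary oxygen therapy* (including all types of oxygen therapy) until Days 6, 14, and 28". The cumulative form is deliberate. The summary of changes for Version 3.0 says so: "the need of auxiliary oxygen therapy is sufficient for this endpoint and clarified that this proportion will be assessed not on but until Days". The current text agrees.

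**Entry state.** Section 9.2, criterion 4, admits two groups. One is "Category 4: Hospitalized, virus-positive, oxygen by mask or nasal prongs (excluding high-flow oxygen therapy) with the following conditions" on saturation and respiratory rate. The other is Category 3: hospitalized, "virus-positive, no oxygen therapy with the following condition", where that condition concerns only the reason for hospitalization. Criterion 5 asks for "Presence of at least 1 symptom characteristic for COVID-19 disease i.e., fever, cough or respiratory distress".

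**Recovery.** The same list has the proportion "with clinical recovery defined as" a temperature limit by site of measurement, a respiratory rate of at most 24 per minute and an oxygen saturation of at least 98%, the last two without oxygen. It also has "Time to clinical recovery". Neither entry states that the definition must be unmet at baseline, and the proportion has no assessment day.

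**Status.** Section 16.3.1 makes all Part 1 endpoints descriptive and, in Part 2, everything other than primary and key secondary endpoints exploratory. Neither endpoint is among the activity endpoints in Section 16.4.2. Section 8.1 stratifies randomization by age and antiviral therapy, not by entry category.

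**The concern.** A binary endpoint that counts any oxygen up to a given day, with no rule for oxygen already in use, gives a patient on oxygen at entry the same answer whatever the treatment does. Those patients add equal numbers to both arms and pull the comparison toward no difference. Any chance difference between arms in the Category 4 share also feeds directly into the result.

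The stake is interpretation. Oxygenation and clinical recovery are examples named in the secondary efficacy objective, and Part 2 endpoints are to be reconsidered after the main analysis of Part 1. A near-null oxygen result could be read as absence of effect when much of it was fixed by the definition.

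**Working it through.** The plan states no figure for either endpoint, so there is none to reproduce. The check is one of definitions, followed by an illustration.

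**Step 1: oxygen by entry category.**
- Category 4: on oxygen at entry, any type counts, cumulative to Days 6, 14 and 28. The value is 1 at all three times in both arms, and the within-category difference is exactly 0.
- Category 3: no oxygen at entry. The value is 1 only if oxygen is needed later, so this group is informative.

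**Step 2: dilution.** Let c be the Category 4 share and q the proportion of Category 3 patients with new oxygen need. Then

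overall proportion = c + (1 − c) × q, and difference between arms = (1 − c) × (q on placebo − q on IMU-838).

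The documents give neither c nor q. Assumption: q = 0.30 on placebo and 0.20 on IMU-838. In Category 3 alone, OR = (0.20/0.80)/(0.30/0.70) = 0.58.

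| c | Placebo | IMU-838 | Difference | OR |
|---|---|---|---|---|
| 0.30 | 51% | 44% | 7 points | 0.75 |
| 0.50 | 65% | 60% | 5 points | 0.81 |
| 0.60 | 72% | 68% | 4 points | 0.83 |
| 0.75 | 82.5% | 80% | 2.5 points | 0.85 |

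For example, at c = 0.50: 0.50 + 0.50 × 0.30 = 0.65; 0.50 + 0.50 × 0.20 = 0.60; OR = (0.60/0.40)/(0.65/0.35) = 0.81.

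**Step 3: does restricting to Category 3 lose more than it gains?** Take 100 patients per arm (Section 16.1) and the 2-sided 90% interval (Section 16.3.1). The approximate chance that the interval excludes no difference in favour of IMU-838 is

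Φ{ [d√n − 1.645 √(2 p̄(1 − p̄))] / √(p0(1 − p0) + p1(1 − p1)) },

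where p0 and p1 are the proportions in the two arms, d is their difference and p̄ their mean. Use n = 100 for all patients and n = 100(1 − c) for Category 3 only.

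| Category 3 rates (assumed) | c | All patients | Category 3 only |
|---|---|---|---|
| 30% vs 20% | 0.50 | 18% | 31% |
| 30% vs 20% | 0.60 | 15% | 27% |
| 30% vs 20% | 0.75 | 12% | 20% |
| 40% vs 20% | 0.30 | 63% | 83% |
| 40% vs 20% | 0.50 | 44% | 71% |
| 40% vs 20% | 0.70 | 27% | 52% |

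Restriction gains sensitivity in every row despite the smaller n.

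**Step 4: chance imbalance.** With 100 per arm and c = 0.50, the standard deviation of the between-arm difference in Category 4 share is √(2 × 0.25/100) = 0.071. One point of imbalance moves the endpoint by (1 − q) points, so at q = 0.30 one standard deviation moves it by 0.70 × 7.1 = 5 points. That equals the whole diluted effect at c = 0.50. This is noise rather than bias, but analysis by entry category would remove it.

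**Step 5: recovery at entry.** Category 3 sets no limit on temperature, respiratory rate or saturation, and cough alone satisfies criterion 5. An afebrile patient with cough, a normal respiratory rate and a saturation of 98% on room air is eligible. That patient meets the recovery definition on Day 0, with time to recovery of 0 in either arm. Category 4 patients cannot, because the definition requires no oxygen. The documents do not allow a count of such patients.

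**The case against.** **No decision rests on either endpoint.** Both are absent from the activity list, Part 1 has no formal tests, and Part 2 would treat them as exploratory. The secondary objective names oxygenation and recovery only as examples. All of this stands and limits the consequence.

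**Weaning is measured elsewhere.** A reader might infer that the plan cannot show faster weaning in Category 4. The documents do not support that. Section 7 also lists duration of auxiliary oxygen therapy and change in daily WHO status, where coming off low-flow oxygen in hospital is a move from 4 to 3. Time to clinical improvement includes live discharge without oxygen. The flaw belongs to one endpoint, not to the plan's coverage of oxygen.

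**Detail is deferred.** Section 16.3.1 leaves the full description of analyses to a statistical analysis plan whose detailed rules are not in the text reviewed, so a later baseline rule cannot be excluded. For the same reason, a reader might infer that one transient normal reading is enough for recovery, but that is drawn from silence. The protocol wording still contains no baseline rule for either endpoint.

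**The gain is limited.** Under 30% vs 20%, Category 3 alone reaches only 20% to 31% in Step 3, so either version would usually be inconclusive. That is true, but the restricted version is better in each case and estimates something interpretable.

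**Recovery is the weaker half.** It touches only Category 3 patients who meet all three limits together while hospitalized for medical reasons. This also stands.

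**Conclusion.** The point holds for the oxygen endpoint as worded. It is fixed for every patient on oxygen at entry, so its treatment information comes only from Category 3. The fixed value follows from the definitions and needs no assumption. The size of the dilution does: it rests on an unknown Category 4 share and on assumed Category 3 rates. With 30% vs 20%, the odds ratio moves from 0.58 to between 0.81 and 0.85 for Category 4 shares of 50% to 75%.

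For clinical recovery the logic holds, but only for Category 3 patients who already meet all three limits, and the effect is unquantified. A reader might infer that recovery is uninformative throughout Category 3. It is not: patients with fever, fast breathing or saturation below 98% still contribute. Nor does the point affect the decision to start Part 2. It is a worthwhile clarification of secondary endpoints with modest consequence.

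**What to change.** **Oxygen.** Replace the single proportion in Sections 1 and 7, and in the statistical analysis plan, with two, reported alongside the existing duration-of-oxygen endpoint:
- (a) among patients in Category 3 at baseline, the proportion starting any oxygen by Days 6, 14 and 28;
- (b) among patients in Category 4 at baseline, the proportion alive and off oxygen on Days 6, 14 and 28.

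The data are already scheduled in Table 3: WHO score at screening, and oxygen and survival status during treatment, on Day 14 and on Day 28.

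**Recovery.** Analyse the proportion with recovery and the time to it in patients who do not meet all three criteria at the Day 0 pre-dose assessment. Confirmation at a second assessment should be at most a sensitivity analysis. Section 12.3 omits saturation from the Day 6 and Day 14 documentation list for discharged patients, and Table 3, as it reads in the text available, shows no temperature, respiratory rate or saturation on Day 28. Some true recoveries could therefore not be confirmed.

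**Cost.** Endpoint wording and analysis-plan text, with no new data for the main analyses. The downside is a smaller denominator for each endpoint.
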